10.1	Study Design/Study Endpoints	17
10.2	Sample Size and Accrual	18
10.3	Data Analyses Plans.....	19

11.0	STUDY MANAGEMENT	19
11.1	Conflict of Interest.....	19
11.2	Institutional Review Board (IRB) Approval and Consent.....	19
11.3	Registration Procedures	20
11.4	Subject Compensation.....	19
11.5	Data Management and Monitoring/Auditing	20
11.6	Adherence to the Protocol	20
11.7	Amendments to the Protocol	21
11.8	Record Retention.....	21
11.9	Obligations of Investigators	21
12.0	REFERENCES	23
13.0	APPENDICES.....	24

LIST OF ABBREVIATIONS

CKD	chronic kidney disease
CBC	complete blood counts
CVD	cardiovascular disease
ESRD	end-stage renal disease
FGF23	fibroblast growth factor 23 hormone
LVH	left ventricular hypertrophy
NPT2b	sodium phosphate co-transporter
PTH	parathyroid hormone
FEPi	Fractional excretion of phosphate
P1NP	N terminal propeptide of Type 1 procollagen, bone formation marker
CTX	C terminal cross-linked peptide, bone resorption marker
LC	Lanthanum Carbonate
N	Nicotinamide

STUDY SCHEMA

LC, Lanthanum carbonate

N, Nicotinamide

STUDY SUMMARY

Title	EFFECTS OF NICOTINAMIDE AND LANTHANUM CARBONATE ON PHOSPHORUS HOMEOSTASIS
Short Title	Nicotinamide, lanthanum carbonate and phosphate homeostasis
Protocol Number	The standard protocol number used to identify this study
Phase	Phase 1, detailed physiologic study
Methodology	double blind, randomized, placebo-controlled, 2x2 factorial
Study Duration	12-18 months (to complete the entire study protocol)
Study Center(s)	Single-center
Objectives	Define short-term effects of the interventions (lanthanum carbonate and nicotinamide) on indices of phosphate handling
Number of Subjects	80
Diagnosis and Main Inclusion Criteria	Healthy volunteers
Study Product(s), Dose, Route, Regimen	Nicotinamide, 750 mg by mouth twice daily Lanthanum carbonate, Fosrenol, 1000 mg by mouth three times daily with meals
Duration of administration	2 weeks (length of time study participants are enrolled in study)
Reference therapy	reference is a placebo
Statistical Methodology	Repeated measures analysis using mixed linear models

1.0 BACKGROUND AND RATIONALE

1.1 Disease Background

Chronic kidney disease (CKD) is a growing public health problem that increases risks of end-stage renal disease (ESRD), cardiovascular disease (CVD), fractures, and death, and it poses an enormous financial burden on the US health system.¹⁻³ Existing therapies modestly impact outcomes.⁴⁻⁸ Novel strategies targeting CKD-specific mechanisms are urgently needed to improve health and reduce cost.

CKD is complicated by disordered mineral metabolism, characterized by abnormal calcium and phosphate homeostasis, calcitriol and klotho deficiency, and elevated levels of parathyroid hormone (PTH) and fibroblast growth factor 23 (FGF23).⁹ Elevated FGF23 is the earliest and most common manifestation of disordered mineral metabolism.¹⁰ Observational studies report independent associations between elevated phosphate and FGF23 blood levels and increased risks of ESRD, CVD and death.¹¹⁻¹³ As potential explanatory mechanisms, phosphate excess induces arterial stiffness due to vascular calcification, and FGF23 excess contributes directly to the pathogenesis of left ventricular hypertrophy (LVH).^{14,15} Together, these effects promote CVD events and death.¹²

Dietary phosphate absorption is a modifiable determinant of phosphate and FGF23 levels.¹⁶⁻¹⁸ Small studies of short duration suggest that phosphate binders and dietary phosphate modification in CKD can lower phosphate and FGF23 blood levels by reducing paracellular absorption of phosphate in the gut.¹⁹ However, animal studies demonstrate that compensatory upregulation of transcellular phosphate absorption via the sodium phosphate co-transporter, NPT2b, reduces the efficacy of these approaches.^{20,21} Since nicotinamide lowers plasma phosphate by reducing gut expression of NPT2b,²² we hypothesize that use of nicotinamide combined with phosphate binders on a background of dietary phosphate moderation will most effectively reduce phosphate and FGF23 blood levels in CKD. We plan to advance this approach in future randomized clinical trials.

The objective of this study is to perform a detailed physiologic study of healthy volunteers to assess the short-term effects of nicotinamide alone, lanthanum carbonate alone, or both in combination, on phosphate homeostasis. The results from healthy volunteers will provide information needed for optimal design of studies for patients with CKD.

1.2 Study Agent(s)/Devices Background and Associated Known Toxicities

Nicotinamide will be used at a dose of 750 mg twice daily. Nicotinamide reduces plasma phosphate levels by blocking intestinal phosphate absorption through down-regulation of NPT2b,²¹ and it is well-tolerated and considered safe at high doses.²³ Unlike niacin, nicotinamide does not cause flushing, and is thought to be less likely to cause liver test abnormalities, hyperuricemia, or insulin resistance.²⁴ In a post-hoc analysis of a randomized study of niacin in 327 patients with CKD stages 2 and 3, Rao et al found that, in addition to reducing phosphate levels in the blood, niacin decreased FGF23 levels by 10.9% from baseline over 24 weeks, and that the magnitude of the decline in FGF23 was directly associated with the magnitude of decline in blood phosphate.²⁵

Lanthanum carbonate at a dose of 1000 mg twice daily with meals will be used. Lanthanum carbonate is a phosphate binder that is approved for use in patients with ESRD undergoing dialysis. This fixed dose was chosen because we have demonstrated that this dose safely reduced urinary phosphate, signifying effective phosphate binding, in CKD stages 3-4.^{26,27} Importantly, lanthanum carbonate has been used in the hemodialysis population, with 6-year long safety data demonstrating a good safety profile.²⁸ Lanthanum carbonate has also been

used in healthy volunteers in whom it has also been found to be safe. As in patients with CKD, doses of 1000 mg three times daily in healthy volunteers achieve maximal reduction in 24-hour urine.²⁹

1.3 Other Agents/Devices

N/A

1.4 Rationale

The justification for the combined approach of binders with nicotinamide to modify plasma phosphate and FGF23 levels in CKD is rooted in our current understanding of the underlying biology. However, detailed human physiologic studies investigating the joint effects of these agents on blood and urine levels of mineral metabolites are not available in health or in CKD. Animal data consistently demonstrate that nicotinamide blocks small bowel Pi absorption by decreasing protein levels of NaPi2b.^{20,21} Some studies also suggest that nicotinamide may block phosphate reabsorption at the renal proximal tubule,³⁰ but this has not been studied in detail in healthy volunteers or CKD patients. Finally, the effects of nicotinamide on FGF23, PTH, calcitriol, and other parameters of mineral metabolism are unexplored in humans. Therefore, our proposed study will fill critical gaps that are needed to advance this novel therapeutic approach into future clinical trials.

We propose to study healthy volunteers because detailed data on the effects on mineral metabolism of nicotinamide alone or in combination with binders in this population are not available. In the future, we will also extend the proposed studies to patients with CKD.

Given that 24-hr urinary phosphate excretion declines and fractional phosphate excretion rises with progressive CKD, an additional justification for the study of healthy volunteers is the ability to easily detect changes following proposed interventions in both 24-hour and fractional urinary phosphate excretion.

For this detailed physiologic study, we chose to use the 2x2 factorial study design because we are specifically interested in investigating the effects of the combined interventions as compared to the effects of the placebo and to each monotherapy group.

We chose plasma phosphate, 24-hour urine phosphate, fractional urinary excretion of phosphate (FePI), FGF23 and PTH as end-points because we are interested in the effects of the interventions on phosphate handling and mineral metabolism (See Table). Additional end-points will include markers of bone turnover, including N terminal propeptide of Type 1 procollagen (P1NP) and C terminal cross-linked peptide (CTX) to assess the influence of the interventions on bone metabolism.

Summary of End Points			
End-Point	Primary	Secondary	Justification
Plasma Phosphate	X		Marker of phosphate handling
24-hr Urine Phosphate	X		Marker of phosphate handling
FePI	X		Marker of phosphate handling
PTH		X	Hormonal regulator of mineral metabolism
FGF23		X	Hormonal regulator of mineral metabolism
P1NP		X	Bone formation marker
CTX		X	Bone resorption marker

2.0 STUDY OBJECTIVES

2.1 Primary Objectives

2.1.1 To determine the short-term effects of lanthanum carbonate and nicotinamide, alone and in combination, on phosphate handling, as measured by plasma phosphate, 24-hour urinary phosphate and fractional excretion of phosphate in healthy volunteers

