10.2 Sample Size and Accrual

Assumptions based on prior studies:

- Data on effects of nicotinamide on blood or urine phosphate in healthy volunteers are not available.
- Similarly, data on the combined use of the nicotinamide and lanthanum carbonate are lacking.
- Therefore, we relied on published data of the effects on lanthanum carbonate on 24-hour urine phosphate. In previous short-term studies of healthy volunteers, lanthanum carbonate at the dose that we will use in our study decreased 24-hour urine phosphate by 236 to 468 mg/day.²⁹ The within group standard deviation of change in 24-hour urine phosphate ranged from 168 to 294 mg/day.²⁹

Derivation of the sample size for this study:

Using the PS Power and Sample Size calculator (independent t test), we estimated that a sample size of 20 participants per group will yield 80% power to detect a difference of 273 mg/dl in urine phosphate, at $\alpha=0.05$, assuming a within group SD of the change in 24-hour urine phosphate of 300 mg/day. Assuming a conservative within group SD of the change in plasma phosphate of 0.55 mg/dl, the sample size of 20 volunteers per group will allow us to detect a difference as small as 0.50 mg/dl in plasma phosphate.

Importantly, we based our power calculations on t-tests that compare pre to post intervention changes across two groups. Because the repeated measures analyses we will employ using linear mixed models will reduce within-subject variability, we expect to have more power than is tabulated above and view the presented power calculations as conservative estimates. Additionally, power for main effects analyses (effects of lanthanum carbonate alone and nicotinamide alone; 40 participants per groups; margin comparison) will be greater than the presented power for comparisons of dual treatment to placebo (20 participants per group; individual cell comparison).

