10.3 Data Analyses Plans

- We will study changes over time in absolute levels of the primary and secondary end-points.
- We will use mixed-model, repeated-measures analyses to assess the changes.
- Model terms will include:
 - fixed-effects treatment terms (treatment group);
 - the interaction between each treatment and time (nicotinamide x time and lanthanum carbonate x time);
 - the interaction between treatments (nicotinamide x lanthanum carbonate);
 - the interaction between treatments and time (nicotinamide x lanthanum carbonate x time);
 - random-effects terms, connoting individual participants.
- If the interaction term between treatments and time (nicotinamide x lanthanum carbonate x time) is significant, we will compare the response in the dual intervention group to the placebo group.
- If the interaction term between treatments and time (nicotinamide x lanthanum carbonate x time) is not significant, we will examine the main effects of each intervention.
- We will use natural log transformation for end points with skewed distribution.
- If there are significant differences ($p<0.05$) in age, gender and baseline eGFR across randomized treatment groups, we will adjust for these covariates.
- Standard descriptive analyses will be used for safety evaluations.

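### Do the three unranked primary end points in Section 10.3 need a multiplicity rule?

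*Combined protocol and SAP*

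**What the plan says.** The primary objective in Section 2.1 is to determine the effects of both drugs, alone and together, "as measured by plasma phosphate, 24-hour urinary phosphate and fractional excretion of phosphate in healthy volunteers". The end-point tables in Sections 1.4, 2.3 and 10.1 mark all three as primary and rank none. The schedule in Section 5.5 has a co-primary heading over the urine and FePI rows. Plasma phosphate is listed under a different heading, and no rule goes with the label.

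Section 10.3 opens with "We will study changes over time in absolute levels of the primary and secondary end-points" and fits a repeated-measures mixed model. If the three-way term (nicotinamide by lanthanum by time) "is significant, we will compare the response in the dual intervention group to the placebo group"; if it "is not significant, we will examine the main effects of each intervention". No level is given for these tests. The only p-value threshold in that section concerns baseline differences "in age, gender and baseline eGFR across randomized treatment groups, we will adjust for these covariates".

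Section 10.2 uses an alpha of 0.05, one end point at a time. It states that "20 participants per group will yield 80% power to detect a difference of 273 mg/dl in urine phosphate", gives a matching figure for plasma phosphate and gives none for FePI. It adds that "power for main effects analyses (effects of lanthanum carbonate alone and nicotinamide alone; 40 participants per groups; margin comparison") will exceed the power of the 20-per-group comparison.

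**The concern.** Three primary end points under one objective, each tested at 0.05, give a drug three chances to succeed. If one success is enough to say that the drug changes phosphate handling, the error rate of that statement exceeds 5%. Nothing in Section 10.3 says whether one, all or each separately is meant, and the co-primary label does not settle it.

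Section 1.1 says the results will inform the design of later CKD studies. A chance finding, most plausibly for nicotinamide, could therefore carry forward. Section 10.2 says there are no healthy-volunteer data on nicotinamide and blood or urine phosphate against which to check it.

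**Working it through.** **Inputs.** From Sections 10.1 and 10.2: 20 per cell, 40 per margin, alpha 0.05 (taken as two-sided), SD of change 300 mg/day for urine phosphate and 0.55 mg/dl for plasma phosphate. The urine difference of 273 is printed in mg/dl but is read as mg/day, the unit of its SD. Assumed, because the documents give no value: correlations among the end points from 0 to 0.9, and a 0.05 interaction test applied separately to each end point. Change scores stand in for the drug-by-time terms.

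**The plan's own figure.** Two-sided t test, 20 v 20, 38 degrees of freedom:
- urine: 273/300 = 0.91 SD, power 80.1%;
- plasma: 0.50/0.55 = 0.909 SD, power 80.0%.

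Both reproduce the stated 80%. They are per end point, unadjusted, and take no account of the interaction step.

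**One end point, one drug, as written.** With cells ordered dual, lanthanum only, nicotinamide only, placebo, the lanthanum contrast is (1, 1, -1, -1) and the interaction contrast is (1, -1, -1, 1). Their product sums to 1 - 1 + 1 - 1 = 0, so with equal cells they are independent. The false-positive rate is 0.95 × 0.05 = 0.0475.

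**Any one of three, no effect on any.** At correlation 0 the rate is 1 - (1 - 0.0475)³ = 0.136, or 1 - 0.95³ = 0.143 without the interaction step. Simulation at other correlations, after the interaction step:

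| Correlation | One drug | Either drug |
|---|---|---|
| 0 | 13.6% | 25.3% |
| 0.5 | 12.0% | 22.6% |
| 0.8 | 9.5% | 18.0% |
| 0.9 | 8.1% | 15.5% |

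The one-drug rate is 7.1% at correlation 0.95 and 4.7% at 1.0.

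**Other readings.**
- All three required: about 0.01% at correlation 0, 0.3% at 0.5 and 2.0% at 0.9. There is no inflation.
- Dual v placebo: the contrast (1, 0, 0, -1) is also independent of the interaction contrast (1 - 1 = 0), so each end point contributes 0.05 × 0.05 = 0.0025. Any of three at correlation 0 gives 1 - (1 - 0.0025)³ = 0.0075; simulation over the correlation range gives 0.6% to 0.9%.
- Lanthanum: Section 10.2 reports that "lanthanum carbonate at the dose that we will use in our study decreased 24-hour urine phosphate by 236 to 468 mg/day", so the case of no effect on any end point does not fit this drug. If only urine phosphate responds, a false plasma or FePI result has probability 1 - (1 - 0.0475)² = 0.093 at correlation 0, falling to about 7% at 0.9.

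**What a correction would cost.** Main effect, 40 v 40, SD 300, comparing 0.05 with the strictest Holm step, 0.05/3 = 0.0167:

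| True difference | Power at 0.05 | Power at 0.0167 | Loss |
|---|---|---|---|
| 273 mg/day | 98.0% | 94.5% | 3.5 points |
| 236 mg/day | 93.5% | 85.5% | 8.0 points |

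With no true interaction, multiplying by 0.95 for the interaction step gives 93.1% and 89.8% at 273 mg/day, and 88.8% and 81.2% at 236 mg/day. Holm within each drug brings the any-one rate to between 2.8% and 4.6% per drug. Over both drugs it is still 5.6% to 8.9%.

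**The case for a change.** The case for a change is a serious one. The plan argues in terms of power and alpha and calls three end points primary, so a reader may expect the error rate to be controlled across them. The interaction step hardly helps: it only multiplies each end point's error by 0.95. A rule would need wording alone, with no added participants or samples, and main-effect power at the low end of the cited lanthanum range would stay above 80% even after the interaction step.

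Most of that stands as description. The rule is absent, the any-one arithmetic is right, and the power loss is bearable. It does not show that following the plan gives a wrong result. The inflation belongs to a composite claim that the plan never makes. The Study Summary describes a Phase 1 physiologic study meant to define short-term effects, with no pass/fail decision attached. Section 1.4 raises gut absorption and renal tubular reabsorption as separate possible actions of nicotinamide, and justifies healthy volunteers by the chance to see changes in both 24-hour and fractional excretion. That favours reading the pattern across three measures over counting any single success. Holm would also need a convention for an end point that the interaction step sends to dual v placebo. Controlling error per drug and not over both drugs would itself be a matter of preference.

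**Conclusion.** No change to the plan is needed. The gap is a missing statement of how the three primaries are read together. The natural way to fill it is to report each end point separately, with its own estimate and unadjusted p-value, and to make no claim that rests on whichever one is significant. On that reading the false-positive rate is about 5% for each end point and drug (4.75% after the interaction step).

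The 8% to 14% per drug arises only if three conditions hold together: an any-one claim is made, the drug affects none of the three measures, and the correlations lie between 0 and 0.9. It does not apply to dual v placebo or to an all-three reading, and its null case does not fit lanthanum. A formal correction is a trade-off on which reasonable statisticians would differ: 3.5 to 8 points of main-effect power before the interaction step, in exchange for partial control of a claim the plan does not make. The mg/dl unit on the 273 figure is a clerical slip and does not affect the conclusion.

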2.2 Secondary Objectives

2.2.1 To determine the short-term effects of lanthanum carbonate and nicotinamide, alone and in combination, on hormonal regulators of mineral metabolism: FGF23 and PTH

2.2.2 To determine the short-term effects of lanthanum carbonate and nicotinamide, alone and in combination, on markers of bone turnover: P1NP and CTX

2.3 Endpoints

Summary of End Points			
End-Point	Primary	Secondary	Justification
Plasma Phosphate	X		Marker of phosphate handling
24-hr Urine Phosphate	X		Marker of phosphate handling
FePI	X		Marker of phosphate handling
PTH		X	Hormonal regulator of mineral metabolism
FGF23		X	Hormonal regulator of mineral metabolism
P1NP		X	Bone formation marker
CTX		X	Bone resorption marker

3.0 PATIENT ELIGIBILITY

Subjects must meet all of the inclusion and exclusion criteria to be registered to the study. Study treatment may not begin until a subject is registered.

3.1 Inclusion Criteria

3.1.1 Healthy volunteers

3.1.2 Age \geq 18 years, at the time of screening

3.1.3 Normal renal function at screening, as defined by

- eGFR > 60
- no albuminuria
- normal urinalysis
- normotensive, defined as blood pressure $< 140/85\text{mmHg}$
- no known history of CKD

3.1.4 Adequate organ and marrow function at screening as defined below:

- HCT	$\geq 30\%$
- platelets	$\geq 125,000/\text{mm}^3$

- total bilirubin	within normal institutional limits
- AST(SGOT)/ALT(SPGT)	$\leq 2.5 \times$ institutional upper limit
- 25-hydroxyvitamin D	$\geq 10\text{mg/dL}$

3.1.5 Women of child-bearing potential and men must agree to use adequate contraception (hormonal or barrier method of birth control; abstinence) prior to study entry, for the duration of study participation, and for 90 days following completion of therapy.

3.1.6 Ability to understand and the willingness to sign a written informed consent.

3.2 Exclusion Criteria

3.2.1 History of allergic reaction to nicotinamide, niacin (excluding flushing), and/or multivitamin preparations

3.2.2 Liver disease, defined as known cirrhosis by imaging or physician diagnosis, documented alcohol use > 14 drinks/week, or aspartate aminotransferase (AST), alanine aminotransferase (ALT), and/or alkaline phosphatase concentrations > 2 times the upper limit of the local laboratory reference range and/or total bilirubin concentration not within institutional limits.

3.2.3 Creatine kinase (CK) concentrations > 2 times the upper limit of the local laboratory reference range at screening

3.2.4 Major hemorrhagic event within the past six months from screening requiring in-patient admission

3.2.5 Blood or platelet transfusion within the past six months from screening

3.2.6 History of primary hyperparathyroidism

3.2.7 Current, clinically significant malabsorption

3.2.8 Anemia (screening HCT $< 30\%$) at screening

3.2.9 Plasma albumin $< 2.5 \text{ mg/dL}$ at screening

3.2.10 25-hydroxyvitamin D $< 10\text{mg/dL}$ at screening

3.2.11 Inability or unwillingness to travel to study visits, as described in the protocol

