5.2 Screening Procedures

Assessments performed exclusively to determine eligibility for this study will be done only after obtaining informed consent.

The screening procedures include:

5.2.1 *Informed Consent*

Consent form will be reviewed in full with each subject.

5.2.2 *Medical history and Physical Exam*

Complete medical and surgical history will be obtained from each subject, and a physical exam will be performed on each subject.

5.2.3 *Demographics*

Subject will be queried on age, gender, race, and ethnicity

5.2.4 *Review subject eligibility criteria*

Study personnel will review inclusion/exclusion criteria with every subject to determine eligibility.

5.2.5 *Review previous and concomitant medications, including multivitamins*

5.2.6 *Vital signs, height and weight*

Blood pressure, height, and weight will be obtained on each subject.

5.2.7 *Hematology*

CBC

5.2.8 *Plasma chemistries and Serum 25-Hydroxyvitamin D*

To include: albumin, alkaline phosphatase, ALT/SGPT, AST/SGOT, BUN, creatinine, electrolytes (sodium, potassium, chloride, bicarbonate), glucose, and total bilirubin; phosphorus; calcium; CK; and 25-hydroxyvitamin D

5.2.9 *Random urine*

To include: creatinine and albumin

5.2.10 *Supplies for 24-hr urine collection*

5.2.11 *Rapid Urine Pregnancy test (for females of child bearing potential)*

See section 3.1.6.1 for definition.

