5.5 Time and Events Table

Periods	SCREENING	BASELINE		Follow UP				
		F1	F2	F3	F4	F5		
Visits	S1	B1	B2/F0					
Days	-15	-5	-2	0	3	6	9	12
Pregnancy testing	X							
RANDOMIZATION				X				
Distribute drug/placebo (X=21 day supply)				X				
Demographics, medical history, physical exam	X							
Vital signs (blood pressure, height, weight)	X							
Co-Primary end-points								
FePI/ Spot Urine phosphate, calcium, and creatinine		X	X	X	X	X	X	X
24-hr urine phosphate, creatinine, calcium, and urea		X	X	X	X	X	X	X
8 hr urine phosphate, creatinine, calcium, and urea		X						X
Spot Urine (creatinine, albumin)	X							
Other mineral metabolites								
PTH		X	X	X	X	X	X	X
FGF23		X	X	X	X	X	X	X
P1NP (bone metabolism marker)		X						X
CTX (bone metabolism marker)		X						X
25 hydroxyvitamin D	X							
Plasma Phosphate	X	X	X	X	X	X	X	X
Plasma Calcium	X	X	X	X	X	X	X	X
Renal parameters								
Chem 7 (Na, K, Cl, HCO3, BUN, Cr, glucose)	X		X	X	X	X	X	X
Plasma Creatinine		X						
Stored blood samples (optional)		X						X
Stored urine samples (optional)		X						X
CBC, LFTs, CK	X			X	X	X	X	X
Adverse events assessment (labs and GI questionnaire)				X	X	X	X	X
Pill Count				X	X	X	X	X

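### The eligibility limits for 25-hydroxyvitamin D (3.1.4, 3.2.10) and plasma albumin (3.2.9) are printed in mg/dL, the wrong unit for both: a minor labelling error in operative enrolment thresholds

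*Combined protocol and SAP*

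**What the plan says.** Two analytes have numerical eligibility limits in mg/dL.

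- **25-hydroxyvitamin D.** Section 3.1.4 lists a value of at least 10 mg/dL among the inclusion requirements. Section 3.2.10 states the mirror-image exclusion: "25-hydroxyvitamin D $< 10\text{mg/dL}$ at screening".
- **Plasma albumin.** Section 3.2.9 excludes "Plasma albumin $< 2.5 \text{ mg/dL}$ at screening".

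Section 3.0 says that a volunteer has to satisfy every inclusion and exclusion criterion before registration. Both analytes are measured at screening. The chemistry list in section 5.2.8 begins "To include: albumin, alkaline phosphatase, ALT/SGPT, AST/SGOT, BUN, creatinine" and ends "phosphorus; calcium; CK; and 25-hydroxyvitamin D". It gives no units. The row "25 hydroxyvitamin D" in the Time and Events Table (section 5.5) gives none either, and marks that test at screening only. No other section states either limit in a different unit.

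**The concern.** Mg/dL suits neither analyte at the printed numbers, and the two errors run in opposite directions. The vitamin D limit is far too high, so read literally nobody could qualify. The albumin limit is far too low, so read literally it could never exclude anyone.

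What is at stake is whether the written protocol contains a usable entry threshold. For 25-hydroxyvitamin D, sections 3.1.4 and 3.2.10 are the only numerical limits and share the same wrong unit, so neither can be used to correct the other. A monitor checking a screening result against the text would find no correct figure. Vitamin D status is a deliberate entry condition in a mineral-metabolism study with PTH among its secondary endpoints, so the limit should be stated correctly.

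**Working it through.** **Inputs from the documents**

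- 25-hydroxyvitamin D limit: 10 mg/dL (sections 3.1.4 and 3.2.10).
- Plasma albumin limit: 2.5 mg/dL (section 3.2.9).

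**Assumptions, not in the documents**

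- Wide human ranges: 5 to 150 ng/mL for 25-hydroxyvitamin D and 1 to 5 g/dL for albumin.
- Presumed intended limits: 10 ng/mL and 2.5 g/dL, inferred because the printed numbers make sense in those units.

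The plan derives neither limit, so there is no calculation of its own to reproduce. The check is a unit conversion.

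**Step 1: 25-hydroxyvitamin D.** 1 mg = 1,000,000 ng and 1 dL = 100 mL, so 1 mg/dL = 1,000,000 / 100 = 10,000 ng/mL.

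- Printed limit: 10 × 10,000 = 100,000 ng/mL.
- Against the presumed limit: 100,000 / 10 = 10,000 times too high.
- Against the assumed range: 100,000 / 150 = 667 times the top and 100,000 / 5 = 20,000 times the bottom.
- The assumed range in the printed unit is 5 / 10,000 = 0.0005 mg/dL to 150 / 10,000 = 0.015 mg/dL. No value in it reaches 10 mg/dL.

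**Step 2: plasma albumin.** 1 g/dL = 1,000 mg/dL.

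- Printed limit: 2.5 / 1,000 = 0.0025 g/dL.
- Against the presumed limit: 2.5 / 0.0025 = 1,000 times too low.
- The assumed range is 1 / 0.0025 = 400 to 5 / 0.0025 = 2,000 times the printed limit.
- The assumed range in the printed unit is 1,000 to 5,000 mg/dL. No value in it is below 2.5 mg/dL.

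**Step 3: could a lost micro sign explain it?** 10 µg/dL is 100 ng/mL, still 100 / 10 = 10 times the presumed vitamin D limit. For albumin, 2.5 µg/dL would be smaller again than 2.5 mg/dL. A dropped prefix therefore does not rescue either figure, and a misread unit is unlikely to recur in three separate criteria.

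**Step 4: do the presumed units give working limits?** 10 ng/mL lies inside 5 to 150 ng/mL, and 2.5 g/dL lies inside 1 to 5 g/dL. In those units each criterion can separate eligible from ineligible volunteers; in mg/dL neither can.

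**Step 5: does anything downstream use these limits?** Neither analyte is in the endpoint table (sections 2.3 and 10.1), the sample-size assumptions (10.2), the model terms or adjustment covariates (10.3), or the stopping rules (7.6).

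**The case against.** The strongest case against giving this weight is that it has no demonstrated consequence. The trial is single-centre, so sites cannot read the limit differently. The vitamin D error would show itself at the first screening result, because on the literal text that person would be ineligible. The albumin error is less self-revealing, but the participants are healthy volunteers and other criteria already catch likely causes of a very low value: "no albuminuria" in 3.1.3, "Liver disease, defined as known cirrhosis by imaging or physician diagnosis" in 3.2.2 and "Current, clinically significant malabsorption" in 3.2.7. The liver and malabsorption exclusions may bear on low vitamin D as well. The large multipliers measure the size of the slip and say nothing about how many people would be wrongly enrolled or excluded, which is probably none. The replacement units are also inferred.

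Most of this stands, and it is why the point is minor. It does not make the printed limits right. That mg/dL is unworkable does not depend on which replacement the sponsor confirms.

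Two stronger readings are tempting. A reader might infer that the trial could register nobody, or that everyone enrolled was ineligible and the results are compromised. That follows only if staff apply the printed unit literally. The documents give no sign that they would, and nothing in the analysis depends on these limits. A reader might also infer how enrolment on the intended units would be classed as a departure from protocol, whether trivial or serious. The documents do not settle that, and no such classification is claimed here.

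**Conclusion.** The point holds as a minor unit-label error in operative enrolment criteria. As printed, the vitamin D threshold is 10,000 times the presumed one and the albumin threshold is one thousandth of it. Read literally, the first bars every volunteer and the second bars none. Those literal consequences rest on the assumed ranges, but the nearest assumed values are still 667-fold (vitamin D) and 400-fold (albumin) away from the printed limits, so no choice within the ranges changes the result. The size of the factors rests on the presumed intended limits, which the documents do not state.

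This is a drafting error in a threshold, not a faulty calculation in the plan. Endpoints, sample size, power, analysis and stopping rules are unaffected.

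**What to change.** Amend the unit in three places: sections 3.1.4 and 3.2.10, presumably to 10 ng/mL for 25-hydroxyvitamin D, and section 3.2.9, presumably to 2.5 g/dL for plasma albumin. The sponsor should confirm the intended values first. The analytes need different units, so a single search-and-replace would not do. Sections 3.1.4 and 3.2.10 should be changed together so that they remain complementary.

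The cost is three labels in a written amendment, which under section 11.7 goes to the IRB before it is implemented. No test, visit or participant is added.
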